*Survey and Randomization Procedures:* Separate surveys were conducted for parents and teens at baseline (at time of enrollment), and at 6, 12 and 18 months later. After both parent and teen completed the baseline survey, families were randomly assigned to either the intervention or control condition using a computer-generated program. Automated e-mails and texts were sent to invite families to complete the follow-up surveys. One week after follow-up survey invitations were sent, reminder e-mails and texts were sent to families who had not completed the surveys, with the e-mails/texts repeated after another week of nonresponse. One week later, separate phone calls were made to parents and teens if they had still not completed. Participants could complete the surveys up to 2 months after surveys were initiated. Of the 411 enrolled dyads, 315 teens (76.6%) and 364 parents (88.6%) completed the 6-month follow-up surveys, and 311 teens (75.7%) and 354 parents (86.1%) completed the 12-month follow-up surveys and 309 teens (75.2%) and 357 parents (86.9%) completed the 18-month follow-up surveys.

*Measures:* Measurement of assignment to condition (experimental vs. control) was based upon the original randomized assignment. Program dosage (no exposure, exposure to alcohol component, exposure to relationship component) was based upon tracking progress through the program, automated in the online delivery.

*Teen alcohol use.* Alcohol items were adapted from the National Longitudinal Study of Adolescent Health (Harris et al., 2008) and asked in surveys. Teens first reported whether they had consumed alcohol over the past 6 months and past 30 days (1 = Yes, 0 = No).

*Quantity and frequency of alcohol use.* Teens reported their frequency of drinking over the past 30 days and past 6 months (0 = Never, 1 = once a month, 2 = 2–3 times a month, 3 = once a week, 4 = 2–3 times a week, and 5 = daily or almost daily). The variable was recoded to more closely approximate the actual number of times used over the time period. For example, 2–3 times a month in the last 30 days was recoded to 2.5, whereas 2–3 times a month over the past 6 months was recoded to 15 (2.5 = 6 months). Teens also reported the usual amount they drank on drinking days (0 = less than one to 7 = more than six).

*Drunkenness:* To assess drunkenness, teens reported the number of times they had gotten “drunk or very, very high” on alcohol over the time period (e.g., past 6 months, past 30 days).

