### **Analyses:**

Descriptive analyses were conducted first to describe rates and mean scores of outcomes overall and by condition across three assessments to check the randomization.

Selection model: Because families chose how much of the intervention to which they were exposed, we conducted a probit analysis predicting whether or not a family completed the alcohol or relationship component from baseline measures. Based on this analysis, an instrumental variable, inverse Mills’ ratio (IMR) representing the underlying selection processes was included as a covariate in our primary dosage analyses (Heckman, 1979). The IMR (non-selection hazard) was calculated in Stata using the two-step procedure described in Heckman (1979). When the IMR is significant in a model, this indicates that the predicted probability of completing the component is associated with the outcome. That is, the same factors that predispose families to complete (or not complete) the component are related to the outcomes. In models where dosage is significant, this indicates that even accounting for factors that are related to completing the program, that dosage is still related to outcomes.

Conducting analyses in SPSS 21, dichotomous outcomes were examined using multiple logistic regression, while continuous outcomes were examined using multiple linear regression. Listwise deletion was used for missing cases. For all regression analyses, the baseline value of the outcome variable, teen gender, teen age, and teen ethnicity, an inverse Mills’ ratio and intervention condition, were covariates to determine whether dosage predicted the outcome for a specific follow-up period (i.e., 6, 12 18 months).

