### **Assessment of Efficacy-Overview:**

Results from the Smart Choices 4 Teens program indicate efficacy for prevention of alcohol use and alcohol-related problem behaviors for older teens when parents and teens, with greater exposure to the program content producing better outcomes, when controlling for baseline rates and selection bias. The intervention also showed efficacy for parent–teen communication, especially around conversations related to social host laws. Further parents and teens engaged in the program were less likely to discuss ways that teens could drink “safely,” and thus not providing a message that teens could drink if they drank safely. Of particular importance is that the dosage effects were noted across different alcohol involvement indicators and some of these impacts persisted at the 12-month follow-up period, showing that the program may have sustained effects.

For the relationships/sexual behaviors component of the intervention, the data support the efficacy of the Smart Choices 4 Teens intervention in increasing adolescent and parent communications about sexual relationships (eg, frequency) and to increase parental guidance (eg, dating rules) when controlling for baseline rates and selection bias. There was some support that the intervention had a main effect on frequency of communication and dating rules set for the adolescents, even after controlling for other adolescent characteristics that were also significant predictors of adolescents’ reports of sexual communication with their parents, including developmental changes over time, as well as adolescent gender, sexual minority status, and sexual experience.

There were indications that the intervention had impact on sexual communication over time, irrespective of the gender of the adolescent. When accounting for the possible interaction between the time of administration, gender of the adolescent, and exposure to the intervention, demonstrated an impact on the parent-teen sexual communication outcome. The intervention increased parent-teen communications regarding increased dating rules, indicating greater parental monitoring of teen relationships. There was no indication of an interaction effect between gender and intervention exposure on dating rules. Participating in the intervention increased the dating rules for all participants and was durable across time.

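### Analyses specifies only wave-by-wave complete-case regressions, which estimate no change in effect over time; the longitudinal model implied by the over-time and durability statements is not described

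*Combined protocol and SAP*

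**What the plan says.** The Analyses section of the combined protocol and SAP is the only place where the outcome models are set out.

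- **Model type:** "dichotomous outcomes were examined using multiple logistic regression, while continuous outcomes were examined using multiple linear regression".
- **Time:** the purpose of each regression is "to determine whether dosage predicted the outcome for a specific follow-up period (i.e., 6, 12 18 months".
- **Covariates, stated to apply to every regression:** "the baseline value of the outcome variable, teen gender, teen age, and teen ethnicity, an inverse Mills’ ratio and intervention condition, were covariates". The list has no wave term, no product of wave with dosage or condition, and no allowance for repeated measurements on the same teen.
- **Missing data:** "Listwise deletion was used for missing cases".

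Follow-up is reported under Survey and Randomization Procedures: "Of the 411 enrolled dyads, 315 teens (76.6%) and 364 parents (88.6%) completed the 6-month follow-up surveys". The 12-month counts are 311 teens (75.7%) with 354 parents (86.1%). At 18 months they are 309 teens (75.2%) with 357 parents (86.9%).

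Assessment of Efficacy-Overview makes two statements about time. For alcohol outcomes: "some of these impacts persisted at the 12-month follow-up period, showing that the program may have sustained effects". For dating rules: "Participating in the intervention increased the dating rules for all participants and was durable across time". The same section mentions an interaction of time of administration, gender and exposure. It also mentions adjustment for developmental change over time, sexual minority status and sexual experience.

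**The concern.** Whether an effect lasts is a question about the later effect and about the difference between waves. A set of separate regressions gives an estimate at each wave but no estimate or interval for that difference. If durability is claimed, the reader needs to know which model supports it, how that model handles repeated answers from one teen, and what it assumes about missing waves. Analyses supplies none of this.

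Listwise deletion within each wave adds two problems. It ignores what a teen's other waves say about a missing one. It also lets the analysed sample change from wave to wave, so a difference between two wave estimates may partly reflect who answered.

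**Working it through.** **1. Reproduce the plan's retention figures (411 dyads).**

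| Wave | Teens | Teens missing | Parents | Parents missing |
|---|---|---|---|---|
| 6 months | 315/411 = 76.6% | 96 (23.4%) | 364/411 = 88.6% | 47 |
| 12 months | 311/411 = 75.7% | 100 (24.3%) | 354/411 = 86.1% | 57 |
| 18 months | 309/411 = 75.2% | 102 (24.8%) | 357/411 = 86.9% | 54 |

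All six percentages match. For teen-reported outcomes, listwise deletion removes at least 96, 100 and 102 teens, before any item or covariate is missing.

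**2. How far the waves can differ in membership.** Overlap is not reported, so only bounds are available.

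- Both 6 and 12 months: at least 315 + 311 − 411 = 215, at most 311.
- All three follow-ups: at least 315 + 311 + 309 − 2 × 411 = 113, at most 309.
- No follow-up: at most 96. It could be 0, since 96 + 100 + 102 = 298 is below 411.
- Some but not all follow-ups: at least 411 − 309 − 96 = 6, at most 411 − 113 − 0 = 298.

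The last range is the group for whom a repeated-measures model gains most over separate fits.

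**3. Compare the stated models with the stated conclusions.**

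| Statement in the efficacy overview | What the models in Analyses provide |
|---|---|
| Some alcohol effects seen at 12 months, hedged | A baseline-adjusted test of association at 12 months, so within reach |
| Dating-rules effect lasting over time, unhedged | An estimate at each wave; no contrast between waves |
| Interaction of time, gender and exposure | No time term and no interaction |
| Adjustment for sexual minority status and sexual experience | Neither is in the covariate list given for all regressions |

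**4. Illustration of what the missing contrast could show.** The documents give no effect size, SD, arm sizes, alpha or between-wave correlation. The following are assumptions: equal arms, two-sided 0.05, outcome in SD units, and correlation ρ between the 6- and 12-month effect estimates of 0.3 to 0.7. With 315/2 = 157.5 and 311/2 = 155.5 teens per arm:

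Var(6) = 2/157.5 = 0.01270; Var(12) = 2/155.5 = 0.01286.

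SE(change) = √[Var(6) + Var(12) − 2ρ√(Var(6) × Var(12))].

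At ρ = 0.5: √(0.02556 − 0.01278) = 0.113, so the 95% half-width is 1.96 × 0.113 = 0.22 SD. At ρ = 0.3 it is 0.26 and at ρ = 0.7 it is 0.17.

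Suppose an effect of 0.3 SD at 6 months halves by 12 months. Both waves would still be significant with probability 0.23 to 0.26, and a direct test of the change would have power of only 0.20 to 0.40. So significance at both waves does not exclude a large decline, and a non-significant interaction does not establish durability. The dosage contrast is less balanced than equal arms (49.5% and 42.7% of intervention families completed the two components), so its precision would probably be lower.

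**The case against.** A reader might infer that durability was concluded by comparing significance at one wave with significance at another, and that it has no test behind it. The documents do not support that. The efficacy overview reports no p-values and no pattern of significance by wave. The durability sentence concerns dating rules, and its paragraph reports an analysis with a time interaction, so it cannot be tied to the regressions in Analyses. Further detail is left to a report and publications outside these documents.

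A reader might also infer that the 12-month alcohol statement is unsupported. It is not: a baseline-adjusted 12-month regression tests for an association at 12 months, and the sentence is hedged.

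The benefit of a joint model is also uncertain. If non-response is nearly nested, about 96 teens have no follow-up at all, and the model adds information for only 315 − 311 = 4 teens at 12 months and 315 − 309 = 6 at 18 months. Parent-reported alcohol communication has higher retention (86.1% to 88.6% at the two follow-ups listed for it).

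These objections limit the point but do not remove it. If a longitudinal model was used, Analyses omits its time terms, correlation structure and missing-data handling, and gives a covariate list for all regressions that does not match it. If none was used, the durability statement has no between-wave estimate. The correction is the same in either case.

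**Conclusion.** The point holds in this form: the specified models are wave-specific and complete-case, they test for an effect at each wave, and they do not estimate maintenance or change. The over-time conclusions need a model that the results section implies and Analyses does not specify.

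The firm figures are the plan's own: 96, 100 and 102 of 411 teens missing, and between 113 and 309 teens with all three follow-ups. The figures for the change between waves (half-width 0.17 to 0.26 SD, power 0.20 to 0.40 to detect a halving of 0.3 SD) rest wholly on assumed inputs and only illustrate scale. The documents do not show that any reported effect is wrong or that it faded. This is a correction that should be made: it replaces the stated method with a better one, and goes beyond asking for more detail.

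**What to change.** For each outcome, replace the separate listwise-deletion fits with one repeated-measures model over 6, 12 and 18 months that uses every available wave.

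- **Continuous outcomes:** linear mixed model.
- **Binary outcomes:** mixed logistic model, or GEE with weighting or multiple imputation.
- **Terms:** condition, wave, condition × wave, the baseline outcome and the stated covariates; add exposure and exposure × wave where dosage is analysed. List any further covariates actually used, such as sexual minority status and sexual experience.
- **Missing data:** state the missing-at-random assumption and report how many teens answered none, some and all of the follow-ups.
- **Reporting:** give the effect at each wave and the change between waves, each with a confidence interval. A wave-averaged effect is optional.
- **Wording:** base any durability statement on the 18-month effect together with the estimated change, not on a non-significant interaction alone. Measures lists alcohol communication only to 12 months, so there the 12-month effect is the last available. Failing this, limit Assessment of Efficacy-Overview to effects at each wave.

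If a longitudinal model was already fitted, describe it in Analyses and reconcile its covariates with the stated list.

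The cost is revised SAP text and some re-analysis of data already held. The downside is reliance on missing at random, which the data cannot verify. The gain in information may be small if few teens answered only some follow-ups, but the between-wave contrast is obtained in any case.

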### **Assessment of Efficacy-Overview:**

Results from the Smart Choices 4 Teens program indicate efficacy for prevention of alcohol use and alcohol-related problem behaviors for older teens when parents and teens, with greater exposure to the program content producing better outcomes, when controlling for baseline rates and selection bias. The intervention also showed efficacy for parent–teen communication, especially around conversations related to social host laws. Further parents and teens engaged in the program were less likely to discuss ways that teens could drink “safely,” and thus not providing a message that teens could drink if they drank safely. Of particular importance is that the dosage effects were noted across different alcohol involvement indicators and some of these impacts persisted at the 12-month follow-up period, showing that the program may have sustained effects.

For the relationships/sexual behaviors component of the intervention, the data support the efficacy of the Smart Choices 4 Teens intervention in increasing adolescent and parent communications about sexual relationships (eg, frequency) and to increase parental guidance (eg, dating rules) when controlling for baseline rates and selection bias. There was some support that the intervention had a main effect on frequency of communication and dating rules set for the adolescents, even after controlling for other adolescent characteristics that were also significant predictors of adolescents’ reports of sexual communication with their parents, including developmental changes over time, as well as adolescent gender, sexual minority status, and sexual experience.

There were indications that the intervention had impact on sexual communication over time, irrespective of the gender of the adolescent. When accounting for the possible interaction between the time of administration, gender of the adolescent, and exposure to the intervention, demonstrated an impact on the parent-teen sexual communication outcome. The intervention increased parent-teen communications regarding increased dating rules, indicating greater parental monitoring of teen relationships. There was no indication of an interaction effect between gender and intervention exposure on dating rules. Participating in the intervention increased the dating rules for all participants and was durable across time.

Further details for the efficacy of the intervention are detailed in the online report of findings and publications.

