Smart Choices 4 Teens required that parents and teens complete the activities online separately. Following completion of the component, teens and parents discussed scenarios reflecting teen choices regarding alcohol use and relationships as an offline activity. Families had to indicate that they had completed the discussion to move on to the next component. In addition, as the program is family based, families could only progress to the next component if their other participating family member had also completed that component. For example, if a teen had completed the Communication component, but their parent had not, the teen would not be able to begin the Alcohol component until their parent had also completed the Communication component. On average, the Communication component took families 20.29 min to complete (21.83 minutes for parents, 18.75 minutes for teens). The Alcohol component took 15.94 min (16.34 minutes for parents, 15.53 minutes for teens), and the Relationship component took 19.75 min (19.79 minutes for parents, 19.71 minutes for teens). The amount of time spent in family discussions of the scenarios is not included in these averages.

**Description of the Control Condition:** Families in both the control and intervention condition received links to resources, including hotline numbers and websites to provide information about teen alcohol and drug use, sexual behavior, suicide, and other health issues. The websites provided contact information for crises, as well as information about the specific health issue (e.g., the Mothers Against Drunk Driving website provided information about rates and consequences of impaired driving). All families also had access to an 800 number throughout the duration of the project to contact with the research team.

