**Selection and Exclusion of Subjects:** Participants were recruited from November 2014 to November 2015 from two online panel vendors to provide a sample that would reflect the national population (Wang-Schweig et al., 2019). Panel members provided demographic characteristics when joining the panel, which were used to determine eligibility for the trial. Panel vendors provided contact information for 1,531 adult panelists via a secure shared website. Among these, 559 were found to be eligible, that is, parent with a teen aged 16–17; English speaking; and a device (tablet or computer) compatible with viewing the online intervention. The research team performed a second level of verification, which entailed calling

and speaking to both parent and teen to verify their eligibility via phone after passing the screener. We were unable to contact 607 panelists to complete this second level of verification, another 365 were not eligible, and 148 declined to participate. Among the 559 eligible panelists, 411 (73.5% of eligible adults) completed baseline online surveys (and their teens completed separate online surveys) and enrolled in the study. Parents were consented for their own and their teen's participation in the program and the surveys. Assent forms were completed by teens prior to engaging in any exposure to treatment or surveys. Each participant received US \$30 for baseline surveys, US \$40 for 6-month follow-up surveys, and US \$50 each for 12-month and 18-month follow-up surveys via a mailed check.

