### **Exposure to Treatment**

Concerns about Recruitment: Because the intervention is available online, families could complete the intervention in their own homes, at a time convenient for them. Thus, some of the typical barriers to participation were removed. Despite these barrier reductions, only half (49.5%) of the families assigned to the intervention condition completed the program materials on teen alcohol use and less than half (42.7%) completed the materials on romantic/sexual relationships.

There are many reasons for prevention strategies to fall short of this total “inoculation” of the general population. First, families whose teens are perceived as “doing fine” or “not in need of any prevention” are difficult to engage in prevention. Second, parents sometimes believe that it is important not to prevent risky behaviors of teens like drinking and sexual activity but rather to teach teens how to engage in these behaviors while minimizing risks; they may not view a prevention program as aligned with their parental values. Third, families with teens who are already engaged in heavy alcohol consumption and/or engaged in risky sexual behaviors need a more intensive treatment intervention. Fortunately, there does not need to be total saturation of the general population for community-level perspectives to change. Nonetheless, an efficacious intervention that reaches even a sizeable proportion of the general population does potentially provide a resource to a sizeable number of families. Furthermore, parents of older teens do express a desire for some support and help in managing these “adult” behaviors.

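### The reported exposure effect is a self-selected completer comparison: efficacy should rest on the randomised contrast, with no graded-dose claim

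*Combined protocol and SAP*

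**What the plan says.** All places are in the combined protocol and SAP.

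- **Assessment of Efficacy-Overview** reports efficacy for alcohol outcomes, "with greater exposure to the program content producing better outcomes", qualified as adjusted for baseline levels and selection. It singles out the dosage effects as especially important.
- **Measures** (under Study Design) defines exposure at three levels: "Program dosage (no exposure, exposure to alcohol component, exposure to relationship component". How these levels are coded in the regressions is not stated.
- **Exposure to Treatment** says that "only half (49.5%) of the families assigned to the intervention condition completed the program materials on teen alcohol use" and that "less than half (42.7%) completed the materials on romantic/sexual relationships".
- **Description of the Intervention** lists the components as Communication, Alcohol, Relationships, and says that "families could only progress to the next component if their other participating family member had also completed that component".
- **Survey and Randomization Procedures** says that "families were randomly assigned to either the intervention or control condition using a computer-generated program". Neither the allocation ratio nor the arm sizes are given.
- **Analyses** acknowledges that exposure was the families' own choice. It fits a probit model for component completion and carries an inverse Mills' ratio into the dosage regressions, which it treats as primary. Randomised condition enters those regressions as a covariate, with the baseline value of the outcome and teen gender, age and ethnicity. Missing cases are deleted listwise. Comparison by condition without dosage is described only at the descriptive level.

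**The concern.** The efficacy statement uses causal wording and speaks of more exposure giving more benefit. Two features of the design stand in its way.

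First, sequential access with little drop-off between the second and third components leaves the middle dosage level almost empty. A dosage effect then says little about whether more of the program does more good. It mainly compares families who finished with families who did not.

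Second, finishing was not randomised. Exposure to Treatment itself names reasons for not engaging that bear on the outcomes: teens thought to be doing well, parents who prefer to teach moderation, and teens already drinking heavily. These need not bias the comparison in one direction, but any of them could produce a difference between completers and non-completers without a program effect.

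At stake is the main alcohol conclusion. The trial has a randomised comparison that could carry it, yet the overview rests it on a comparison that randomisation does not protect.

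**Working it through.** **Inputs.** 411 dyads enrolled ("411 (73.5% of eligible adults) completed baseline online surveys"; 411/559 = 73.5%, which checks). Alcohol completion 49.5% and Relationship completion 42.7% (Exposure to Treatment). Teen follow-up 76.6%, 75.7% and 75.2% at 6, 12 and 18 months (Survey and Randomization Procedures). Assumptions: near-equal arms; Alcohol before Relationships, so that every Relationship completer is also an Alcohol completer; follow-up equal across dosage levels.

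**1. Whole counts that reproduce the stated percentages.** Near-equal arm sizes that give both 49.5% and 42.7% after rounding:

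| Intervention arm | Alcohol | Relationship | Alcohol only | Neither |
|---|---|---|---|---|
| 192 | 95 | 82 | 13 | 97 |
| 206 | 102 | 88 | 14 | 104 |
| 218 | 108 | 93 | 15 | 110 |
| 220 | 109 | 94 | 15 | 111 |

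An arm of 205 does not fit. Very unequal allocations also fit: an arm of 103 would give 7 Alcohol-only families, and an arm of 309 would give 21.

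**2. Overlap and intermediate dose.** Overlap = 42.7/49.5 = 86.3% (86.1% to 86.5% allowing for rounding), whatever the arm size. Intermediate dose = 49.5% - 42.7% = 6.8% of the arm. The dosage distribution is therefore 50.5% neither, 6.8% Alcohol only and 42.7% both.

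**3. After follow-up.** For an arm of 206, 14 x 0.766 = 10.7 and 14 x 0.752 = 10.5, so about 11 intermediate families with teen data at each wave. Across the table the range is 13 x 0.752 = 9.8 to 15 x 0.766 = 11.5.

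**4. What a dosage slope would measure.** As an illustration only, score the levels 0, 1, 2 and ignore the other covariates.

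- Mean score = 0.068 x 1 + 0.427 x 2 = 0.922.
- Sum of squares per family = 0.505 x 0.922² + 0.068 x 0.078² + 0.427 x 1.078² = 0.429 + 0.0004 + 0.496 = 0.926.
- Weight on each group mean: neither, -0.505 x 0.922/0.926 = -0.503; Alcohol only, 0.068 x 0.078/0.926 = 0.006; both, 0.427 x 1.078/0.926 = 0.497.

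The slope is half the difference between both and neither, and the middle group hardly enters. If the levels were instead fitted as separate categories, the middle estimate would rest on the 10 to 11 or so families in step 3.

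**5. What the dosage and condition terms mean together.** Write the model as outcome = b0 + b1 x condition + b2 x dosage + covariates. Controls were offered only resource links, so presumably all have dosage zero. Apart from shared covariates, controls inform b0, b1 compares intervention families at dosage zero with controls, and b2 compares families within the intervention arm. Neither b1 nor b2 is the randomised effect. With dosage as a yes/no Alcohol indicator and covariates balanced, the randomised effect is b1 + 0.495 x b2. Having condition in the dosage model therefore does not supply the randomised contrast.

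**The case against.** The strongest reply is that the overview says greater exposure, and completers against non-completers is a contrast of greater with lesser exposure. With an arm of 206 it has about 102 against 104 families before attrition and does not depend on the 14. That stands. A reader might infer from the thin middle level that no exposure statement can be supported; the documents do not bear that out. An adjusted association with completion can be estimated. What fails is the graded reading and the causal verb.

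It can also be said that selection is disclosed and adjusted for. That stands too, and the overview says so. But the adjustment is a model, not randomisation, and the plan names no predictor of completion that is left out of the outcome regressions. Whether the adjustment suffices is a separate question; the point here is that the dosage claim depends on it.

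A further stronger reading would be that the plan explicitly claims separate Alcohol and Relationship effects. The sentence beginning "For the relationships/sexual behaviors component of the intervention, the data support the efficacy" goes on to credit the whole intervention and later mentions a main effect. Results are grouped by component, but no separation is claimed.

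Nor do the documents support a charge of collinearity between two completion indicators, or of low power for both components against Alcohol only. They describe neither a model containing both indicators nor that comparison.

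Finally, the middle count is inferred. The text spells out the order only for Communication before Alcohol, and families who did Communication alone or part of a component are not counted and appear to fall under no exposure. This limits the precision of the count, but it does not supply a gradient.

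**Conclusion.** The concern holds in a limited form. The documents support at most an association, after adjustment, between completing and not completing the program. They do not support a graded dose-response, because the intermediate level holds about 6.8% of the intervention arm, or some 13 to 15 families. They do not support a causal reading of exposure, because the dosage term is a self-selected comparison within one arm.

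The 86% overlap and the 6.8% rest on the components having been taken in the listed order. The count also rests on near-equal arms, and the analysed number on similar follow-up across dosage levels. The within-arm point needs only that controls had no access to the program.

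Under the same order no family completed Relationships without Alcohol, so the data could not separate the two components. That is a limit to respect in reporting, not a claim the overview has made. Nothing here shows that the program had no effect. The documents do not give the results needed to say what the randomised contrast would show.

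**What to change.** 1. Fit the regressions described under Analyses with randomised condition, the baseline value of the outcome and teen gender, age and ethnicity, but without dosage or the inverse Mills' ratio, for each outcome at each follow-up. Take the efficacy statement from the condition term. State that this analysis was moved to the lead position after the dosage results were known, and that it still covers respondents only, because of listwise deletion.
2. Report the dosage models as secondary and non-causal, with the number of families at each level and the coding used.
3. Reword the efficacy overview to say that completers differed from non-completers after adjustment. Make no graded-dose claim and no claim that separates the Alcohol and Relationship components.

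The cost is one extra set of regressions on data already collected, plus rewording. No new data are needed. It does change which analysis leads, since Analyses now gives that place to dosage, and the efficacy statement may become less favourable.
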